4.1. Enrollment Eligibility Criteria

4.1.1. Inclusion Criteria

Individuals who meet all of the following criteria are eligible for enrollment as study participants:

1. Subject must be able to understand and provide informed consent
2. Age ≥ 18 years of age at the time of study entry
3. Recipients of non-HLA identical living or deceased donor renal transplants
4. Protocol renal allograft biopsy at 5 months (± 8 weeks) after transplantation with Banff i1 and/or ti1 with concomitant t scores t0, t1, t2 or t3; Banff i2 and/or ti2 with concomitant t scores t0 or t1; and without v > 0, [ptc + g] ≥ 2 , C4d > 1 (by IF), or C4d > 0 (by IHC); confirmed by central pathologist. Subjects must not be treated for pathologic criteria (e.g. steroids).
5. eGFR ≥ 30 ml/min at the time of study entry
6. Maintenance immunosuppression consisting of tacrolimus, MMF/MPA \pm prednisone (≤ 10 mg/day)
7. Current immunizations including TdAP, pneumococcal and seasonal influenza vaccines prior to study treatment, completed prior to randomization and no less than 14 days prior to planned manufacturing collection.
8. Hepatitis B serologies must be the following:
 - a. Positive HB surface antibody, negative HB core antibody and negative HB surface antigen for recipients immune to hepatitis B
 - b. Negative HB surface antibody, negative HB core antibody and negative HB surface antigen for non-immune/ HBV naïve recipients provided donor had negative HB core antibody and negative HB surface antigen at the time of donation
9. Negative TB test (PPD, interferon-gamma release assay, ELISPOT) within 1 year prior to enrollment. Subjects with a history of latent TB (positive TB test without active infection) must have completed one of the current latent TB infection treatment regimens endorsed by the CDC (Division of TB Elimination, 2016).
10. Women of childbearing potential must have reviewed Mycophenolate REMS and have a negative pregnancy test upon study entry
11. Female subjects with child-bearing potential, must agree to use FDA approved methods of birth control for the duration of the study; subjects must consult with their physician and determine the most suitable method(s) that are greater than 80% effective (<http://www.fda.gov/birthcontrol>)

4.1.2 Exclusion Criteria

Individuals who meet any of these criteria are not eligible for enrollment as study participants:

1. Inability or unwillingness of a participant to give written informed consent or comply with study protocol
2. History of malignancy; except adequately treated basal cell carcinoma
3. History of graft loss from acute rejection within 1 year after any previous transplant
4. History of transplant renal artery stenosis
5. History of cellular rejection prior to enrollment that did not respond to steroids and/or subsequent creatinine after treatment for rejection greater than 15% above baseline
6. Known hypersensitivity to mTOR inhibitors or contraindication to everolimus (including history of wound healing complications)
7. Any chronic illness requiring uninterrupted anti-coagulation after kidney transplantation
8. Post-transplant DSA >5000 MFI or post-transplant treatment with IVIg for DSA. Enrolled subjects with post-transplant DSA >2000 MFI will not be eligible for mTOR conversion.
9. Positive HIV 1 or HIV 2 serology prior to transplantation
10. Known positive HBSAg, or HBcAB serology
11. Proteinuria with urine pr/cr > 1.0 g/g
12. Any condition requiring chronic use of corticosteroids >10mg/day at the time of study entry
13. Subjects requiring treatment for pathologic findings on study eligibility biopsy (see inclusion 4).
14. Active infection at the time of study entry
15. History of active TB or latent TB without adequate treatment (see inclusion 10)
16. Serum BK virus >1,000 copies/ml by PCR at the time of study entry
17. Hematocrit <27%; ANC < 1,000/ μ L; lymphocytes <500/ μ L at the time of study entry
18. Participation in any other studies with investigational drugs or regimens in the preceding year
19. Any condition or prior treatment which, in the opinion of the investigator, precludes study participation
20. Unable to provide adequate biopsy specimen (paraffin embedded formalin fixed) from eligibility biopsy (3-7 months post-transplant) for quantitative analysis.
21. EBV naïve recipient of a kidney from an EBV positive donor, historically EBV naïve recipient with primary EBV infection at the time of screening (primary anti-VCA IgM, without antibody to EBNA), positive EBV PCR
22. Hepatitis C Virus Ab positive subjects with negative HCV PCR are eligible if they have spontaneously cleared infection or are in sustained virologic remission for at least 12 weeks after treatment.
23. Positive SARS-CoV2 testing by RT- PCR

4.2. Treg Infusion Eligibility Criteria

4.2.1. Treg Infusion Inclusion Criteria

1. Individuals randomized to group 2 who continue to meet all of the enrollment criteria.
2. Negative SARS-COV2 RTPCR within 1 week of Treg infusion

4.2.2. Treg Infusion Exclusion Criteria

Individuals randomized to group 2 who meet any of these criteria are not eligible for Treg infusion:

1. Received any vaccination within 14 days prior to blood collection for Treg manufacture
2. Unacceptable Treg product
3. Positive pregnancy test for women of childbearing potential

4.3. mTOR Conversion Eligibility Criteria

4.3.1. mTOR Conversion Inclusion Criteria

Individuals who meet all of these criteria are eligible for mTOR conversion:

1. Received at least 300×10^6 polyTreg infusion
2. Resolution of inflammation on the 2-week post-infusion biopsy as compared to the baseline biopsy, confirmed by central pathologist

4.3.2 mTOR Conversion Exclusion Criterion

Individuals who meet any of these criteria are not eligible for mTOR conversion:

1. Post-transplant DSA >2000 MFI
2. Any condition or clinical variable, which in the opinion of the site investigator, precludes conversion to mTOR.

4.4. Selection of Clinical Sites

All participating centers use immunosuppressive regimens consisting of tacrolimus, MMF/MPA \pm steroids. Based on preliminary data on SCI, 10.9% of those who undergo a protocol kidney biopsy at 6 months will meet histologic criteria for inclusion in the TASK trial. The combined annual volume of both living and deceased kidney transplants at the clinical sites is about 1,927. We are planning to enroll a total of 14 patients, thus requiring a consent rate of approximately 30% which is attainable for the patient population at these clinical centers.

5. Investigational Agent: PolyTregs

5.1. Formulation of PolyTregs

Collection of Recipient T cells

Peripheral blood leukocytes will be collected from eligible participants after eligibility is confirmed. The whole blood or leukapheresed cells will be immediately transported to the manufacturing facility. If the whole blood or leukapheresis product does not produce sufficient numbers of Tregs for infusion, the leukapheresis or phlebotomy may be repeated to ensure an adequate initial cell number for product manufacture.

PolyTregs Expansion

Treg isolated from autologous starting material will be expanded with commercially available anti-CD3 and anti-CD28 magnetic bead for 14 days in cultures containing medium supplemented with deuterated glucose. Blood or leukapheresis product from recipients participating at a clinical site other than UCSF will be shipped at room temperature via next-day service to UCSF for further processing.

5.2. Packaging and Labeling of PolyTregs

At the end of the 14-day expansion of polyTregs, the anti-CD3 and anti-CD28 beads will be removed by magnetic separation. The expanded Tregs will be re-suspended in 100 ml of a solution of 49.02% (v/v) PlasmaLyte-A, 49.02% (v/v) Dextrose 5%, 0.45% NaCl, and 1.96% (v/v) 25% human serum albumin and filled in a sterile infusion bag. The filled product will be refrigerated and quarantined until release.

Prior to release, a product label will be affixed on the infusion bag. The label will provide: the unique product identifier, recommended storage temperature, date of cell harvest, expiration date and time, and clearly indicate the name and unique identifier of the intended recipient. A Certificate of Analysis documenting the test results of release assays will accompany the final product during delivery to the bedside.

The Tregs products manufactured for subjects at an off-site location will be shipped from UCSF to the clinical site via next-day service using validated conditions and containers. Qualified staff at the remote site will receive the polyTregs and verify the recorded shipment temperatures were maintained within the validated range according to UCSF established SOPs.

5.3. Dosage, Preparation, and Administration

Subjects randomized to Group 2 will receive a single infusion of $550 \pm 450 \times 10^6$ polyTregs. Preparations less than 100×10^6 will not be infused. Cells not infused will be used for research.

Pre-medications will be administered 30-60 minutes prior to infusion. Pre-medications will include 650 mg acetaminophen and 25-50 mg diphenhydramine intravenously or by mouth.

After double verification of cell therapy product and recipient identification, the product will be infused via a peripheral intravenous (IV) line primed with saline by gravity in approximately 20 to 30 minutes. Following administration of the Treg product, product bag, tubing and peripheral IV line will be flushed with normal saline to ensure the complete dose is infused.

Vitals signs will be monitored before, during, and after the infusion. Emergency medical equipment will be available during the infusion in case the subject has an allergic response or an infusion reaction that can result in a CRS. The IV line

will be maintained after the infusion and the subject will be asked to remain in the clinical research unit for a minimum of 24 hours which will allow ongoing monitoring for any infusion-related signs and symptoms.

5.4. Drug Accountability

Under Title 21 of the Code of Federal Regulations (21CFR §312.62) the investigator will maintain adequate records of the disposition of the investigational agent, including the date and quantity of the drug received, to whom the drug was dispensed (participant-by-participant accounting), and a detailed accounting of any drug accidentally or deliberately destroyed.

Records for receipt, storage, use, and disposition will be maintained by the study site. A drug-dispensing log will be kept current for each participant. This log will contain the identification of each participant and the date and quantity of drug dispensed.

All records regarding the disposition of the investigational product will be available for inspection.

5.5. Toxicity Prevention and Management

5.5.1. Dose Escalation Plan

There is no plan for dose escalation in this trial.

5.5.2. Waiting Period between Infusions

Due to manufacturing constraints, there will be a naturally imposed waiting period of at least 1 week in between infusions. This will provide a window to delay or cancel the next infusion in case a stopping rule has been met. Other than the 1-week manufacturing delay, there will be no mandated waiting period between infusions in the polyTregs treatment arm (Group 2), since the proposed starting dose has been infused safely previously in kidney transplant recipients.

5.6. Premature Discontinuation of PolyTregs

PolyTregs will be stopped and will not be restarted if there is a hypersensitivity reaction, a CTCAE ≥ 3 infusion-related reaction, a CTCAE Grade ≥ 3 CRS, or any other infusion related serious adverse event.

6. Investigational Immunosuppressive Regimen: Everolimus

At the time of Treg infusion, the maintenance immunosuppression will consist of tacrolimus with target levels of 4-11 µg/L, MMF/MPA ± steroids. On the follow-up biopsy 2 weeks after the polyTreg infusion, the inflammatory load will be assessed by computer assisted image analysis calculating the number of infiltrating cells per square mm as well as the percentage of renal cortex infiltrated with lymphocytes. If the inflammation has resolved on the 2 week follow up biopsy as compared to the baseline biopsy, everolimus will be started at 1.5 mg bid and the dose of tacrolimus reduced by 50% for 4 weeks and then discontinued. Target everolimus trough levels will be 3-8 µg/L with concomitant tacrolimus therapy, and 6-10 µg/L once tacrolimus is discontinued. These patients will remain on everolimus, MPA ± prednisone through the end of the trial and the follow-up period. If on the 2-week follow up biopsy, inflammation is still present (even if reduced in intensity compared to the baseline biopsy), no change will be made to the maintenance immunosuppressive regimen.

6.1. Zortress® (Everolimus)

Zortress® is an mTOR inhibitor immunosuppressant manufactured by Novartis Pharmaceuticals Corporation and is commercially available. Zortress® is FDA licensed for the prophylaxis of kidney transplant rejection in adults with low to moderate immunologic risk.

6.1.1. Formulation, Packaging, and Labeling

Everolimus is a macrolide immunosuppressant. Everolimus inhibits antigenic and interleukin (IL-2 and IL-15) stimulated activation and proliferation of T and B lymphocytes. Everolimus is supplied as tablets for oral administration containing 0.25 mg, 0.5 mg, and 0.75 mg of everolimus together with butylated hydroxytoluene, magnesium stearate, lactose monohydrate, hypromellose, crospovidone, and lactose anhydrous as inactive ingredients.

Zortress® tablets are packed in child-resistant blisters. Each strength is available in boxes of 60 tablets (6 blister strips of 10 tablets each). Tablets are white to yellowish, marbled, round, and flat with beveled edges. Tablets should be stored at 25°C (77°F) with excursions permitted to 15-30°C (50-86°F). Tablets should be protected from light and moisture.

6.1.2. Zortress® Prescribing Information (Per Package Insert)

According to the package insert, Zortress® is to be used in combination with basiliximab induction and concurrently with reduced doses of cyclosporine and corticosteroids. An initial everolimus dose of 0.75 mg orally twice daily (1.5 mg/day) is recommended for adult kidney transplant patients in combination with reduced dose cyclosporine, administered as soon as possible after transplantation. Pharmacokinetic studies in kidney transplant patients show that steady-state of everolimus is reached by Day 4. The recommended therapeutic range for everolimus is 3 to 8 ng/mL. Recommended cyclosporine blood concentrations are recommended as follows: 100-200 ng/mL through 1 month after transplant, 75-150 ng/mL at 2 and 3 months after transplant, 50-100 ng/mL at 4 months after transplant, and 25-50 ng/mL from 6 months to 12 months after transplant. Dose adjustments based on everolimus blood concentrations can be made at 4-5 day intervals.

6.1.3. Everolimus Study Dosing and Administration

The use of everolimus in this trial will deviate from package instructions. Subjects in this trial are enrolled between 3 and 7 months after transplantation and induction therapy is site-specific (not study mandated). Furthermore, subjects will be on tacrolimus at study entry, rather than cyclosporine. In eligible patients, everolimus will be initiated within 2 weeks after kidney biopsy showing resolution of inflammation following Treg infusion. Everolimus will be initiated at a dose of 1.5 mg orally twice daily and titrated, as needed. Subjects will begin everolimus with target trough levels of 3-8

$\mu\text{g/L}$ for 4 weeks while still taking tacrolimus. Everolimus target trough levels will be 6-10 $\mu\text{g/L}$ when tacrolimus is discontinued.

6.2. Assessment of Participant Compliance with mTOR and CNI Dosing

Study subjects will have, at a minimum, weekly monitoring of trough levels.

6.3. Toxicity Prevention and Management

In subjects who develop any of the following conditions after initiation of everolimus therapy, everolimus will be discontinued and tacrolimus will be restarted. Target tacrolimus trough levels will be 4-11 mcg/L.

1. Worsening of proteinuria with urine pr/cr >1 g/g
2. Severe hypercholesterolemia (LDL>190 mg/dL or triglycerides >500 mg/dL) not responsive to therapy with lipid lowering agents
3. Severe edema or fluid accumulations such as pleural or pericardial effusions
4. Interstitial pneumonitis
5. Severe mouth ulcers
6. Severe cytopenia (CTCAE grade 3 or higher) not responsive to dose adjustment of everolimus or MMF/ MPA
7. Any condition which in the determination of the investigator requires discontinuation of everolimus therapy such as planned surgery.

6.4. Rejection after Initiation of Everolimus

Any subject with biopsy proven or treated rejection after the start of study mandated everolimus will discontinue everolimus and resume tacrolimus. Target tacrolimus trough levels will be 4-11 mcg/L.

7. Other Medications

7.1. Immunosuppressive Medications

7.1.1. Tacrolimus

Target tacrolimus trough levels for this study prior to conversion to everolimus are 4-11 µg/dl, which falls within standard of care. For eligible subjects in Group 2, the tacrolimus dose will be reduced by 50% when everolimus is initiated. Tacrolimus will be discontinued 4 weeks after initiation of everolimus therapy.

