9.3.1. Risks of Tacrolimus

Post-Transplant Diabetes Mellitus

Insulin-dependent post-transplant diabetes mellitus (PTDM) was reported in 20% of Prograf-treated kidney transplant patients without pretransplant history of diabetes mellitus in the Phase III study. The median time to onset of PTDM was 68 days. Insulin dependence was reversible in 15% of these PTDM patients at one year and in 50% at 2 years post-transplant. Black and Hispanic kidney transplant patients were at an increased risk of development of PTDM.

Nephrotoxicity

Tacrolimus can cause nephrotoxicity, particularly when used in high doses. Nephrotoxicity was reported in approximately 52% of kidney transplantation patients and in 40% and 36% of liver transplantation patients receiving tacrolimus in the U.S. and European randomized trials, respectively, and in 59% of heart transplantation patients in a European randomized trial. In patients with persistent elevations of serum creatinine who are unresponsive to dosage adjustments, consideration should be given to changing to another immunosuppressive therapy. Care should be taken in using tacrolimus with other nephrotoxic drugs.

Hyperkalemia

Mild to severe hyperkalemia was reported in 31% of kidney transplant recipients and in 45% and 13% of liver transplant recipients treated with tacrolimus in the U.S. and European randomized trials, respectively, and in 8% of heart transplant

recipients in a European randomized trial and may require treatment. Serum potassium levels should be monitored and potassium-sparing diuretics should not be used during tacrolimus therapy.

Neurotoxicity

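### Protocol 7.1.1 gives the tacrolimus trough target per decilitre, ten times the per-litre target that section 6 sets before everolimus conversion

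*Protocol*

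**What the plan says.** The protocol states a tacrolimus trough target in four places.

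- **Section 7.1.1 (Tacrolimus):** "Target tacrolimus trough levels for this study prior to conversion to everolimus are 4-11", with µg/dl printed as the unit directly after these digits.
- **Section 6, opening text (everolimus regimen):** at Treg infusion, "the maintenance immunosuppression will consist of tacrolimus with target levels of 4-11 µg/L".
- **Section 6.3 (toxicity after everolimus is started):** tacrolimus is restarted, and "Target tacrolimus trough levels will be 4-11 mcg/L".
- **Section 6.4 (rejection after everolimus is started):** tacrolimus is resumed at the same target as in 6.3, again in mcg/L.

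Everolimus targets in sections 6 and 6.1.3 are also per litre: 3-8 µg/L while tacrolimus continues and 6-10 µg/L afterwards. Section 6.1.2 reports the label range in another unit: "The recommended therapeutic range for everolimus is 3 to 8 ng/mL".

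The SAP states no tacrolimus target of its own. Its section 6.3 lists only when trough levels are monitored.

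**The concern.** Sections 7.1.1 and 6 both set a tacrolimus target for patients who have not yet converted to everolimus, with the same digits and different units. Both cannot be right.

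Section 7.1.1 is the part of the protocol devoted to tacrolimus, so a reader would look there for the target. The per-litre statements all sit in the everolimus chapter and are tied to Treg infusion or to restarting tacrolimus after everolimus. Group 1 has neither, yet Appendix 2 schedules tacrolimus levels for it. If any stated target is meant to apply to Group 1, the one in 7.1.1 is the nearest.

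Two things are at stake. The first is safety: taken literally, 7.1.1 asks for ten times the intended blood level. Section 9.3.1 warns that "Tacrolimus can cause nephrotoxicity, particularly when used in high doses" and links neurological effects to high blood concentrations. The second is the compliance record: protocol section 6.2 uses trough monitoring to assess compliance with CNI dosing. Against the literal range in 7.1.1, every trough in the intended range would count as below target.

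**Working it through.** The target is a specified value, not the result of a sample-size or power formula, so there is no figure to reproduce. The check is a unit conversion and a comparison of sections.

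**Inputs**

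| Section | When it applies | Printed target |
|---|---|---|
| 7.1.1 | Before everolimus conversion | 4-11 µg/dl |
| 6 (opening) | At Treg infusion | 4-11 µg/L |
| 6.3 | Tacrolimus restarted after everolimus toxicity | 4-11 mcg/L |
| 6.4 | Tacrolimus resumed after rejection on everolimus | 4-11 mcg/L |

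**Step 1: do sections 7.1.1 and 6 cover the same period?** Sections 6.1.3 and 8.3 give the order of events: Treg infusion, a biopsy 2 weeks later, then everolimus within 2 weeks of that biopsy if inflammation has resolved. Infusion therefore always precedes conversion, and the target in section 6 falls inside the period covered by 7.1.1. Sections 6.3 and 6.4 concern a later period. They support the choice of unit but are not the direct comparison.

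**Step 2: convert 7.1.1 to per litre.** 1 L = 10 dL, so x µg/dL = 10x µg/L.

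- Lower limit: 4 × 10 = 40 µg/L
- Upper limit: 11 × 10 = 110 µg/L

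**Step 3: compare with section 6.**

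- Ratio at each limit: 40/4 = 10 and 110/11 = 10
- Gap between the ranges: 40/11 = 3.64, so the lowest value in 7.1.1 lies above the highest in section 6

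**Step 4: decide which unit is meant.** Three of the four statements are per litre with identical digits, and only 7.1.1 differs. The sentence in 7.1.1 also says that its range "which falls within standard of care". As a minor further sign, the everolimus targets are per litre too: 1 ng/mL = 1 µg/L, so the label range of 3 to 8 ng/mL equals the study target of 3-8 µg/L.

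**Step 5: apply the correction.** With µg/L in 7.1.1, the section reads 4-11 µg/L (= 4-11 ng/mL = 0.4-1.1 µg/dL), and all four statements agree.

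**The case against.** The strongest reply is that this is a typographical slip which the protocol itself corrects and which has no realistic consequence. Tacrolimus is not an investigational agent here: the Study Definitions page lists only polyTregs and everolimus. Patients are already on maintenance tacrolimus at entry, all centres use it routinely, and levels are measured locally. A transplant team would have to raise an established regimen tenfold against both section 6 and the standard-of-care wording. Nothing is calculated in 7.1.1, so this is an inconsistency of units rather than an arithmetic error, and the factor of 10 measures the misprint, not an effect on patients. The match of periods is also partial: section 6 fixes the target at one moment in Group 2, whereas 7.1.1 covers the whole time before conversion.

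Most of this stands. Misdosing is unlikely, and the statistical plan is untouched. The partial match does not rescue 7.1.1, because at infusion both statements apply and they conflict. It also means that no other section restates the target for the rest of the pre-conversion period. The reply bears on urgency. It does not make the printed unit right.

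**Conclusion.** The point holds. As printed, section 7.1.1 sets a pre-conversion tacrolimus target of 40-110 µg/L, exactly ten times the 4-11 µg/L in section 6 and with no overlap. The slip is in 7.1.1. That conclusion rests only on the protocol's own text and the definition of the units; it needs no outside therapeutic range. The factor of 10 is the size of the printed discrepancy, not an estimate of harm. It should be corrected because it sits in an operative drug-level target, but it does not bear on the validity of the trial, its sample size or any planned analysis.

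**What to change.** In Protocol section 7.1.1, replace µg/dl with µg/L. Leave sections 6, 6.3 and 6.4 as they are.

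The documents do not say whether treatment is complete. If patients are still being treated, send sites a short notice of the correction. If not, record it in the study file and mention it in the study report.

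The cost is one unit in one sentence plus the notice or file note. Neither the design nor the SAP changes.
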